#### **4.3 Concomitant Therapies**

##### **4.3.1 Permitted Therapy**

Subjects will be allowed to continue on the following Crohn's disease-related concomitant medications during the study.

- Oral 5-ASA drugs, if on a stable dose for at least 2 weeks prior to the screening visit (same dosage to be maintained throughout the trial).
- Antidiarrheals (e.g., loperamide) will be assessed at each visit.
- Mercaptopurine, azathioprine, methotrexate, if stable dose for at least 8 weeks prior to the screening visit (same dosage to be maintained throughout the trial).

**Confidential**

---

- Oral steroids (first 8 weeks of Treatment Period only): Prednisolone or prednisone at doses of  $\leq$  20 mg (or equivalent) per day, or a budesonide dose of  $\leq$  9 mg per day are permitted. Subjects must be able to be tapered off steroids by Week 8 of the Treatment Period.

#### **4.3.2 Prohibited Therapy**

Use of the following medications is prohibited within the inclusion/exclusion specified pre-study time-frames and throughout the study unless otherwise noted:

- Corticosteroids: Parenteral and rectal steroids are prohibited from the screening visit through the end of the study.
- Any oral or intravenous antibiotic. NOTE: A short course of antibiotic to treat acute conditions (e.g., sinusitis, urinary tract infection) is permitted.
- Use of any drug from the rifamycin class at any time during study participation, including rifaximin, rifampin, rifapentine, and rifabutin. Current international trade names of rifaximin include: Alfa Normix, Colidimin, Faxinorm, Flonorm, Lormyx, Normix, Refero, Rifacol, Rifax-Aw, Rifaxan-Aw, Spiraxin, Targaxan, Tixtar, Tixteller, Xifaxan, Xifaxanta, and Zaxine.
- Any biologicals (e.g., TNF $\alpha$  inhibitor, natalizumab, or similar drugs)
- Cyclosporine, tacrolimus, sirolimus, mycophenolate mofetil, or similar drugs
- Rectal administration of 5-ASA or corticosteroid enemas/foams/suppositories.
- Use of tube or enteral feeding, elemental diet, or parenteral alimentation.
- Introduction of any new probiotics or similar supplements during the study.
- The introduction of any new medication for the treatment of Crohn's disease is prohibited, unless the medication is required in the Investigator's opinion as rescue medication. Subjects receiving rescue medication will be considered treatment failures but should remain in the study.

All concomitant medications, including those taken 30 days prior to screening visit, will be documented (drug name, start and stop dates, and indication) in the concomitant medication section of the CRF.

#### **4.4 Females of Reproductive Potential**

If a female subject becomes pregnant while participating in this study, the study drug will be immediately discontinued and the subject will be followed until the outcome of the pregnancy is known. The pregnancy will be reported to Salix using the guidelines provided in Section 7.7 and Section 7.8.

Confidential

---

#### **4.5 Premature Subject Discontinuation**

Subjects will be encouraged to complete the study; however, they may voluntarily withdraw at any time. Subjects withdrawn from the study will not be replaced.

A subject may be discontinued from study drug treatment and/or the study for the following reasons:

- Occurrence of an AE and/or SAE, which suggests an unacceptable risk to the subject, in the judgment of the investigator, including worsening of the disease under study.
- Pregnancy (see Section 7.7 for further details).
- Subject request to withdraw.
- Sponsor decision to terminate the study.

For all cases of premature withdrawal from the study listed above or any other, the investigator must provide the reason for discontinuation on the appropriate CRF page. *The investigator should make every attempt to obtain End of Treatment and End of Study assessments, including ileocolonoscopy.*

If treatment with investigational study drug has been prematurely discontinued, the End of Treatment assessments will be completed, and an attempt should be made to have the subject followed for 14 days after last administration of study drug to perform the End of Study assessments.

If a subject prematurely discontinues treatment with investigational drug at any time due to an AE or SAE, the End of Treatment assessments will be completed, and an attempt should be made to have the subject followed at least 14 days to perform the End of Study assessments, or until resolution or stabilization of the condition resulting in withdrawal has been confirmed.

The Investigator may discontinue individual subjects from the study at any time during the study. The investigator must provide the reason for discontinuation on the appropriate CRF page.

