Headache (6% of patients), CD symptoms (6% of patients), nausea (4% of patients), flatulence (2% of patients), nasopharyngitis (2% of patients), and fever (2% of patients) were the most commonly reported drug-related AEs. One case of *C. difficile* infection was diagnosed 20 days after the end of the treatment period in a patient who received Rifaximin EIR 800 mg twice daily. A sudden death during the follow-up period, caused by acute massive bilateral pulmonary edema, was reported in a patient with preexisting concomitant arrhythmia. The death was assessed as unlikely related to the study drug. No clinically significant changes in the results of safety laboratory tests were observed in any study group.

In addition to the studies noted above for Rifaximin EIR, rifaximin has been studied in approximately 5000 subjects in multiple clinical studies in irritable bowel disease (IBS) (N = 1103); and in other therapeutic areas including treatment of travelers' diarrhea (N = 593), travelers' diarrhea prophylaxis (N = 820), acute hepatic encephalopathy (N = 152), and recurrence of hepatic encephalopathy (N = 348). In addition, there is over 20 years of post-marketing experience with the drug.

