### 7.1 Operating Definitions for Assessing Safety

#### 7.1.1 Adverse Event

An AE is any untoward medical occurrence in a subject or clinical investigation subject administered a study product and which does not necessarily have a causal relationship with the treatment.

An AE can therefore be any unfavorable and unintended sign (that could include a clinically significant abnormal laboratory finding), symptom, or disease temporally associated with the use of a study product, without any judgment about causality (i.e., whether or not considered related to the study product).

An AE does include the following:

Confidential

---

- Exacerbation or worsening of a pre-existing illness. NOTE: if the pre-existing illness is the disease under study, then “exacerbation” refers to an unexpected worsening from the condition at baseline.
- Increase in frequency or intensity of a pre-existing episodic event or condition.
- Condition detected or diagnosed after study product administration even though it may have been present prior to the start of the study.
- Symptom associated with disease not previously reported by the subject.

An AE does not include the following:

- Medical or surgical procedures (e.g., surgery, endoscopy, tooth extraction, transfusion) as event terms; the condition that led to the procedure is the AE if it meets the definition of an AE.
- Situations where an untoward medical occurrence has not occurred (e.g., hospitalization for cosmetic elective surgery; and social and/or convenience admissions).
- Overdose of either study product or concurrent medication without any signs or symptoms.
- Symptoms associated with disease, which are consistent with the subject’s usual clinical course; unless the subject experiences worsening of their symptom(s) or the symptom(s) meet the criteria for an SAE.

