7.6 Demographics and Study Summary

7.6.1 Subject Disposition

Subject disposition will be summarized by treatment and study phase and will include the number of subjects entered in the study; number and percentage of subjects who completed or prematurely discontinued (classified by reasons for premature discontinuation); the number of subjects entered in the study at each study site; and the number and percentage of subjects who completed or discontinued at each study site.

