7.8.3.1 Treatment-Emergent Adverse Events

A non-fatal AE is considered as a treatment emergent adverse event (TEAE), if the start date of the AE is within the period of first dose date of study medication and last dose date of study medication plus five days. A fatal AE is considered TEAE if the start date of the AE is within the period of first dose date of study medication and last dose of study medication plus 30 days.

The incidence of treatment-emergent AEs will be summarized by body system and MedDRA preferred term. If a subject reports the same AE more than once, then that subject will only be counted once for the summary of that AE, using the most severe intensity.

In case of incomplete or missing AE dates, the standard Salix estimation rule for AEs will be followed in order to determine whether an AE should be considered treatment-emergent. If the AE category still can't be determined, the AE will be considered as TEAE. The onset dates reported in the CRF will be presented in the listings.

Treatment-emergent AEs will be summarized as follows:

- All treatment-emergent AEs;
- All treatment-emergent AEs by intensity;
- All treatment-emergent AEs related to study drug;
- All treatment-emergent SAEs; and

- All treatment-emergent AEs that led to premature discontinuation of study drug.

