7.8.3.5 Treatment-Emergent Adverse Events Leading to Study Premature Discontinuation

All TEAEs that led to subject discontinuation from the study will be summarized and listed separately.

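### Withdrawals for worsening Crohn's disease are grouped with adverse-event discontinuations, and no planned summary separates them, so the pooled totals mix efficacy failure with intolerance

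*Protocol*

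**What the plan says.** Protocol 4.5 lists an adverse event or serious adverse event, pregnancy, subject request and sponsor decision as grounds for stopping study drug, the study, or both. The first ground covers an event that points to unacceptable risk "in the judgment of the investigator, including worsening of the disease under study". No lack-of-efficacy ground is named, but the list is open: "For all cases of premature withdrawal from the study listed above or any other, the investigator must provide the reason for discontinuation".

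Protocol 7.1.1 limits when Crohn's disease itself is an adverse event. For the disease under study, exacerbation "refers to an unexpected worsening from the condition at baseline". Symptoms in keeping with the subject's usual course are excluded unless they worsen or meet a seriousness criterion. Protocol 4.3.2 classes rescued subjects as treatment failures but keeps them in the study.

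On reporting, SAP 7.6.1 counts subjects who completed or "prematurely discontinued (classified by reasons for premature discontinuation"). SAP 7.8.3.1 summarises events by body system and preferred term and includes "All treatment-emergent AEs that led to premature discontinuation of study drug". SAP 7.8.3.5 then says "All TEAEs that led to subject discontinuation from the study will be summarized and listed separately". Drug-related events have their own table. Neither document plans a discontinuation summary without Crohn's worsening, or one crossed with relatedness.

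**The concern.** Worsening of the disease under study is close to the inverse of the efficacy outcome. If the drug works, more of it is expected on placebo. A withdrawal total that includes it is partly an efficacy result placed in a safety table, and it answers neither question cleanly.

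The comparison at stake is a simple one: how many subjects in each arm stopped because of an adverse event. A reader who takes that total, or the adverse-event line of the disposition table, as a measure of tolerability could be misled in either direction. The overall TEAE and SAE totals carry the same component, because a flare that leads to inpatient admission meets the serious definition in Protocol 7.1.2. The primary test and the sample size are not affected.

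**Working it through.** The plan states no rate, margin or power for adverse-event discontinuation, so there is no figure to reproduce. The check has two parts.

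**1. Where a worsening withdrawal is counted.**

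- A subject whose Crohn's disease worsens unexpectedly and who is judged to be at unacceptable risk falls under the adverse-event ground in Protocol 4.5.
- That subject enters the adverse-event line in SAP 7.6.1, if the site records that reason, and the discontinuation summaries in SAP 7.8.3.1 and 7.8.3.5.
- A subject who stops study drug but stays in the study meets the 7.8.3.1 description (stopping study drug) but not that of 7.8.3.5 (leaving the study). The two summaries need not agree.
- A site could instead record another reason, since the list is open. The same event could then be classified differently between sites.

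**2. What pooling does to the difference.** Let t be the proportion withdrawn for non-Crohn's adverse events and w the proportion withdrawn for Crohn's worsening, with subscripts R (rifaximin) and P (placebo). The two groups are taken as not overlapping.

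- Pooled total in each arm = t + w
- Pooled difference = (t_R − t_P) + (w_R − w_P)
- Exact cancellation when w_P − w_R = t_R − t_P
- 95% CI = difference ± 1.96 × √[p_R(1 − p_R)/n + p_P(1 − p_P)/n]

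Inputs: n = 330 per arm (planned size, Protocol synopsis and SAP 7.3). All withdrawal rates are assumptions. Take t_R = 5% and t_P = 2%, about 16 and 7 subjects. Reported separately, the difference is 3.0 points, with standard error √(0.05×0.95/330 + 0.02×0.98/330) = 0.01426 and 95% CI 0.2 to 5.8.

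| Assumed worsening, R vs P | Pooled total, R vs P | Difference, points (95% CI) |
|---|---|---|
| 2% vs 2% | 7% vs 4% | +3.0 (−0.5 to 6.5) |
| 5% vs 5% | 10% vs 7% | +3.0 (−1.2 to 7.2) |
| 3% vs 5% | 8% vs 7% | +1.0 (−3.0 to 5.0) |
| 4% vs 7% | 9% vs 9% | 0.0 (−4.4 to 4.4) |
| 5% vs 10% | 10% vs 12% | −2.0 (−6.8 to 2.8) |
| 8% vs 5% | 13% vs 7% | +6.0 (1.4 to 10.6) |

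Equal worsening leaves the difference unchanged but widens the interval. More worsening on placebo shrinks, cancels or reverses it. More worsening on drug enlarges it.

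**The case against.** The strongest reply is that the route from treatment failure to an adverse-event withdrawal is narrow and that the tables already let a reader see it.

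- Non-response alone is not an adverse event under 7.1.1, and the ground in 4.5 requires unacceptable risk. This stands. Worsening can still qualify, because 4.5 names it.
- Rescued subjects are meant to stay in the study. This stands for study withdrawal. It does not stop a subject from coming off study drug, which is what 7.8.3.1 counts.
- Other reasons may be recorded, and the CRF codes are not in the documents. This stands, so one cannot say that every worsening withdrawal is booked as an adverse event. It also means that sites may differ.
- Preferred-term rows and listings keep Crohn's events visible, provided worsening is coded as Crohn's disease; Protocol 7.4 asks for the diagnosis rather than its symptoms. This largely stands for the event tables. It does not repair their totals, and the disposition line has no preferred terms.
- Related events have a separate table. It is not crossed with discontinuation, and relatedness is an imperfect filter: Protocol 1.4 lists Crohn's symptoms among the commonest drug-related events in Phase 2, and SAP 7.8.3.3 counts a missing relationship as related.

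A reader might infer that placebo treatment failures fill the tolerability tables and hide a real excess of drug-related withdrawals. The documents do not support that. They give no rate of withdrawal for worsening. The expected 40% and 55% Week 16 success rates in Protocol 8.2 do not supply one, because their complements, 60% and 45%, include subjects who were stable or partly improved. The Phase 2 figure of 6% for Crohn's symptoms has no split by arm and no link to withdrawal.

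**Conclusion.** The point holds as a reporting gap. Crohn's worsening is grouped with adverse-event discontinuation, and no planned summary separates it. Two kinds of figure are affected: pooled event totals and the adverse-event line of disposition. Preferred-term rows and listings are not affected in the same way.

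The size is unknown. The table in the working shows that a 3-point gap in worsening withdrawals in favour of the drug is enough to cancel a 3-point tolerability excess, but both figures are assumed. The direction depends on which arm has more worsening withdrawals, so bias in favour of the drug is conditional on the drug working. SAP 7.3 says that both studies will stop early, so the arms may be smaller than 330 and the intervals wider than those shown. No planned test rests on these totals. This is an inexpensive improvement, not a threat to the trial's main conclusion.

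**What to change.** Change the reporting only, and leave the grounds for stopping treatment in Protocol 4.5 as they are.

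1. Record 'lack of efficacy / worsening of Crohn's disease' as its own discontinuation reason on the CRF and use it in SAP 7.6.1. If data collection has closed, derive it from the recorded reasons and coded terms.
2. In SAP 7.8.3.1 and 7.8.3.5, show TEAEs leading to discontinuation, and the overall TEAE and SAE totals, twice: overall, and excluding Crohn's disease worsening terms. Fix the list of excluded preferred terms before unblinding.
3. Reconcile discontinuation of study drug (SAP 7.8.3.1) with discontinuation from the study (SAP 7.8.3.5), so that each table states which it counts.

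The cost is one reason code or derivation and a few extra table lines, with no new subject assessments. SAP 7.1 already allows supplementary analyses after database lock. The downside is that the tolerability comparison may look slightly less favourable to the drug.

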## 5.0 TREATMENT OF SUBJECTS

### 5.1 Formulation and Supply

Study drug will be supplied by Salix as tablets containing 400 mg Rifaximin DR or matching placebo.

Rifaximin DR will be supplied as pink, coated, oval, biconvex tablets. Each Rifaximin DR tablet will contain 400 mg Rifaximin and the following inactive ingredients: colloidal silicon dioxide, croscarmellose sodium, disodium edetate, hypromellose, magnesium stearate, methacrylic acid and ethylacrylate copolymer, microcrystalline cellulose, propylene glycol, red iron oxide E172, talc, and titanium dioxide.

Matching placebo will be supplied as tablets that are identical in appearance to Rifaximin DR tablets with inactive ingredients. The components used in the manufacturing of the matching placebo tables are: calcium phosphate, colloidal silicon dioxide, corn starch, disodium edetate, hypromellose, magnesium stearate, microcrystalline cellulose, propylene glycol, red iron oxide E172, and titanium dioxide.

Additional details are provided in the Rifaximin IB (39).

### 5.2 Packaging

Salix will supply double-blind study drug in high density polyethylene (HDPE) bottles. Each bottle will contain study drug for 32 days of therapy.

### 5.3 Labeling

The contents of the label will be in accordance with all applicable regulatory requirements and in the official language for each country. Each label may include, but is not limited to, the following information.

- Federal law statement: Caution New Drug-Limited by United States Law to Investigational Use (US only)
- Study number: RECD3126
- Quantity
- Dosing instructions: Take 2 tablets by mouth 2 times a day, approximately every 12 hours.
- Storage information: Store tablets at 20-25°C (68-77°F); excursions permitted to 15-30°C (59-86°F).
- Name, address, and telephone number of the sponsor, contract research organization or investigator
- Study drug, lot number, and expiration or re-test date

**Confidential**

---

- Space for recording visit number, date dispensed, and date returned
- Space for recording subject number and subject initials
- Space for recording investigator name
- "For clinical trial use only" or similar wording
- "Keep out of reach of children"

#### **5.4 Storage and Handling**

All study medication will be kept in a secure storage area with limited access. The secure storage area will be maintained under controlled temperature conditions at 20-25°C (68-77°F); excursions are permitted to 15 to 30°C (59 to 86°F).

#### **5.5 Dosing and Dosing Schedule**

Study medication will be dosed orally as two tablets twice a day (morning and evening, approximately 12 hours apart) with or without food for 52 weeks.

#### **5.6 Rationale for Dose Selection**

The current tablet formulation of Rifaximin EIR was evaluated in a Phase II dose range finding study in 402 subjects with an acute flare of CD (RETIC/03/06). Patients with a CDAI between 220 and 400 points were randomized to 4 treatment groups: Rifaximin EIR 400 mg twice a day, Rifaximin RIR 800 mg BID, Rifaximin EIR 1200 mg BID or placebo BID for 12 weeks. Subjects who achieved clinical remission at the end of the treatment period, defined as CDAI score < 150 points, were admitted to a 3-month follow-up phase. Subjects were allowed to continue stable doses of oral 5-ASA, mercaptopurine, azathioprine, and/or methotrexate as concomitant therapies throughout the study (up to 12 weeks), while the use of antibiotics and oral, intravenous, and rectal steroids were not permitted. As add-on therapy (83% of enrolled subjects were treated with stable doses of 5-ASA and/or methotrexate, azathioprine and mercaptopurine), Rifaximin EIR 800 mg twice a day was statistically superior to placebo in inducing clinical remission (CDAI < 150 points) after 12 weeks of therapy ( $p = 0.007$ ), and maintaining remission for three months after Rifaximin EIR was stopped ( $p = 0.02$ ). In addition, the safety and tolerability of the Rifaximin EIR 800 mg BID regimen in this study was acceptable to warrant further investigation. Based on these data, a dose of 800 mg twice a day was selected for further development.

#### **5.7 Study Drug Accountability**

Only authorized site personnel may dispense study drug. Documentation of investigational drug orders, records of study drug receipt, dispensing, and ongoing study drug inventory will be examined and reconciled throughout the study. Only subjects enrolled in the study may receive study drug, in accordance with all applicable regulatory requirements.

Confidential

---

Study drug reconciliation will be conducted during monitoring visits to ensure appropriate receipt, storage, dispensing, and documentation of returned study drug. Upon completion of the study, this material will be subjected to final inspection and reconciliation.

The following information will be documented regarding study drug:

- Subject number.
- Subject initials.
- Dispensing date and quantity of tablets.
- Initials of study staff dispensing drug.
- Return date and quantity of drug returned by subject.
- Compliance (%) in taking the study drug at each visit.
- Start and stop dates of study drug.

### **5.8 Assessment of Compliance**

After study drug is dispensed, the investigator or his/her representative will count the unused study drug tablets that were returned by the subject at each visit to assess compliance. Study drug compliance will be recorded in the subject's source documentation and CRF. If the subject forgets to return unused study drug at a visit, then compliance will be confirmed after direct questioning of the subject. The investigator's judgment of compliance will be accepted. Attempts to obtain unused study drug should be made at subsequent visits or by the conclusion of the subject's participation in the trial.

Confidential

